One purpose of the pilot study is to collect TEP data for a power analysis because such data does not currently exist. To estimate power for the pilot study, effect sizes for the contrasts of interest in Aims 1 and 2 were estimated from the means and SDs of MEP amplitudes in two published studies that used anodal, 1 mA tDCS to precondition the motor cortex before rTMS was delivered a 1 Hz²⁸ or 5 Hz³ (power estimates for 10 Hz stimulation were based on the 5 Hz study). As in our design, change in cortical

Study Title: Regulating homeostatic plasticity and the physiological response to rTMS
PI: [name]
Institution: University of Arkansas for Medical Sciences
Support: Department of Neurobiology and Dev. Scs.

excitability was measured both immediately following rTMS (acute) and 30 minutes later (lasting effects). PASS 12 was used to calculate power by estimating power, conservatively, as two-sample t-tests (n=5 for all comparisons). For 1 Hz TMS, the power to detect a difference in MEP amplitude between the sham (mean=.89, SD=.08) and active (.64; .08) tDCS conditions was 99% acutely (effect size=2.95) and 48% at 30 minutes (effect size=95%). For the 5 Hz condition, power to detect a difference in MEP amplitude between sham (.99; .16) and active (.98; .16) tDCS was only 6% acutely (effect size=.06) but 100% at 30 minutes (effect size=4.80). Finally, the power to detect a difference in MEP amplitude between 1Hz (.64; .08) and 10Hz (.98; .16) rTMS (after active tDCS preconditioning) was 94% acutely (effect size=2.68) but only 8% at 30 minutes (effect size=.39). Importantly, anodal preconditioning induced LTD (a decrease in the MEP amplitude) in both the 1 and 5 Hz conditions but, consistent with the hypothesis for Aims 1 & 2, the effect was stronger for 1 Hz than 5 Hz rTMS. These estimates give confidence that the sample sizes of our pilot study are sufficient to test Aims 1 & 2.

Aim 3 is being conducted as an open label feasibility study. The data may be used to derive power estimates for future studies. Subjects in this study will have completed sham and active 1 Hz rTMS treatments for tinnitus in a previous study (109033). The length of treatment, time of assessments and ratings of tinnitus used for Aim 3 are based on the previous study (109033). Therefore, we will compare change scores from baseline derived for the ratings of tinnitus in Aim 3 to changes scores from baseline derived from the sham and active 1Hz rTMS treatments in study 109033. HLMs will be used to compare mean scores for each treatment condition to provide an estimate of effect size which can be used for power calculations.

To examine change in cortical excitability following treatment, the LMFP of TEPs derived for regioins of the DLFC and temporal cortex will be compared before and after treatment using paired t-tests.

Ethical Considerations

This study will be conducted in accordance with all applicable government regulations and University of Arkansas for Medical Sciences research policies and procedures. This protocol and any amendments will be submitted and approved by the UAMS Institutional Review Board (IRB) to conduct the study.

The formal consent of each subject, using the IRB-approved consent form, will be obtained before that subject is submitted to any study procedure. All subjects for this study will be provided a consent form describing this study and providing sufficient information in language suitable for subjects to make an informed decision about their participation in this study. The person obtaining consent will thoroughly explain each element of the document and outline the risks and benefits, alternate treatment(s), and

Study Title: Regulating homeostatic plasticity and the physiological response to rTMS
PI: [name]
Institution: University of Arkansas for Medical Sciences
Support: Department of Neurobiology and Dev. Scs.

requirements of the study. The consent process will take place in a quiet and private room, and subjects may take as much time as needed to make a decision about their participation. Participation privacy will be maintained and questions regarding participation will be answered. No coercion or undue influence will be used in the consent process. This consent form must be signed by the subject or legally authorized representative, and the individual obtaining the consent. A copy of the signed consent will be given to the participant, and the informed consent process will be documented in each subject's research record. Subjects will be recruited through direct advertisement. Additionally, we plan to use the Translational Research Institute's ARresearch tool during the recruitment process. We intend to call potential research participants who have provided phone numbers and to send our study advertisement via email to potential research participants who have provided email contact information.

The office of research and regulatory affairs, acting on behalf of the sponsor, UAMS, monitors study procedures independently.

Dissemination of Data

Results of this study may be used for presentations, posters, or publications. The publications will not contain any identifiable information that could be linked to a participant.

Study Title: Regulating homeostatic plasticity and the physiological response to rTMS
PI: [name]
Institution: University of Arkansas for Medical Sciences
Support: Department of Neurobiology and Dev. Scs.

References

Reference List

- (4) Bohning DE. Introduction and overview of TMS physics. In: George MS, Belmaker RH, eds. *Transcranial magnetic stimulation in neuropsychiatry*. Washington, D.C.: American Psychiatric Press; 2000;13-44.

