Specific Aim 1: Determine in normal healthy subjects how increased activation of the TC modifies the induction of LTD by 1 Hz and 10 Hz rTMS. Analyses will examine difference scores between sham and active rTMS in the local mean field power (LMFP) of TEPs (Δ LMFP) recorded from TC and DLFC. Parallel groups of healthy subjects (n=5 each) will receive 1 and 10 Hz rTMS. Four contrasts are of interest – (1) sham vs active tDCS for 1 Hz rTMS, (2) sham vs active tDCS for 10 Hz rTMS, (3) 1 Hz vs 10 Hz rTMS for sham tDCS, and (4) 1 Hz vs 10 Hz rTMS for active tDCS. Our working hypothesis is that increased cortical activation will facilitate LTD following rTMS at both frequencies of stimulation, but the effect for 1Hz will be stronger for than for 10 Hz.

Specific Aim 2: Determine in normal healthy subjects how increased activation of the DLFC modifies LTD induced by 1 Hz and 10 Hz rTMS over the TC. New groups of subjects will be recruited. The design, analyses, and predictions are the same as for Aim 1. The difference is that circuits in the DLFC, a functionally connected network, are being preconditioned rather than TC. We predict that rTMS delivered to the TC will induce LTD in the DLFC after it has been preconditioned with tDCS.

Exploratory Aim. We will develop and test a behavioral model of sound perception in healthy participants who have normal hearing by placing them in a sound attenuated environment and measuring ratings of sounds played above threshold. We will examine how tDCS/rTMS modify these perceptions.

Specific Aim 3: Determine in patient with tinnitus how increased activation of the DLFC modifies LTD and tinnitus perception induced by 1 Hz rTMS over the TC. We will recruit ten subjects from a previous study of rTMS for tinnitus (109033) who agreed to be contacted for future research projects. We will examine change from baseline in TEPs (Δ LMFP) recorded from TC and DLFC and on ratings of tinnitus awareness, annoyance and loudness following three days of treatment (tDCS preconditioning of the DLFC followed by 1 Hz rTMS of the TC). Analyses will examine change from baseline for TEPs and tinnitus ratings. Change scores for tinnitus ratings will be compared to those for sham and active rTMS treatments from a previous study (109033).

Aims 1 & 2 Design: A randomized, blinded, sham controlled, mixed effects model with assignment to two treatment arms (1 or 10 Hz rTMS) and three experimental

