TMS/EEG is used in this proposal to measure the neural activity of targeted circuits. TMS/EEG is a method for probing superficial cortical brain regions to study intra-cortical neural circuits.¹⁹ During TMS/EEG, single (or paired) TMS pulses are delivered repeatedly to a region of the brain while the EEG is being recorded. The data in this proposal will be collected off line, before and after tDCS and rTMS, respectively. TMS evoked EEG potentials (TEPs) can be used to measure cortical excitation/inhibition directly from the cortex. TEPs have high test-retest reproducibility, particularly when stereotaxic systems are used to precisely control the location of TMS delivery from session-to-session.^{20;21} TEPs have been used in conjunction with MEPs to measure LTP induction in the motor cortex of healthy subjects.^{22;23} TEPs are particularly well suited for use in this proposal to assess cortical excitability in non-motor areas, like the TC and DLFC, as well as multiple other locations within and between the cerebral hemispheres. TEPs have the characteristics of a good biomarker of change in neural dynamics. They are easy to obtain, have high test-retest reproducibility, and they have been validated in studies of motor and frontal cortex.²⁰⁻²² TMS/EEG data can also provide information about the ability of stimulated brain regions to generate oscillations in discrete frequency bands of the EEG²⁴ and about the sources and propagation of neural activity in functionally connected brain regions²⁵ which will be examined in exploratory analyses.

Scientific Premise

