Study Design, Population, Apparatus and Investigational Plan

Aims 1 & 2.

Design: This is prospective, experimental design includes a block randomized, blinded, sham controlled, mixed effects model with sequential assignment to two treatment arms (1 or 10 Hz rTMS) and random assignment to three experimental conditions within each arm (Table 1).

Randomization: Subjects will be assigned sequentially to one of two parallel groups (1 Hz or 10 Hz rTMS: Table 1.5). Next, they will complete three experimental test sessions (Table 1). The order of test sessions is randomized. A minimum two week washout period will follow each session to minimize session to session carry forward effects.¹⁵ Washout can exceed two weeks.

[figure not shown]

Figure 1.5. Subject flow.

Study visits: Study visits will be to the transcranial magnetic stimulation laboratory, room 654-2, located on the 6th floor of the Biomedical II research building on the UAMS

Study Title: Regulating homeostatic plasticity and the physiological response to rTMS
 PI: [name]
 Institution: University of Arkansas for Medical Sciences
 Support: Department of Neurobiology and Dev. Scs.

campus. In total, there will be 4 study visits - 1 consent/screening visit and 3 laboratory visits per subject. The 3 laboratory study visits will be separated in time by a minimum of two weeks. The time required to complete a study visit ranges from 1 hour, when TMS/EEG is not collected, to 3.5 hours, when TMS/EEG is collected. TMS/EEG is recorded immediately before and after tDCS preconditioning, immediately following rTMS and after a 20-30-minute delay to examine the acute and lasting effects.

Subject flow: Twenty healthy subjects who meet the entry criteria and pass safety screening for tDCS and TMS will be enrolled (Figure 1.5). Ten subjects will be tested in each aim, with two parallel groups of 5 subjects receiving either 1 or 10 Hz rTMS. Two randomization lists of 10, each balanced between tDCS over TC and tDCS over DLFC, were generated based

on uniformly distributed random number generation in SAS v9.4. The first 10 recruited subjects will receive 1Hz rTMS treatment while the second 10 will receive

Experimental conditions & TMS/EEG assessments.								
Condition†	TMS/EEG	tDCS	TMS/EEG	rTMS	TMS/EEG	30 min delay	TMS/EEG	
1		sham		sham				
2		sham		active				
3		active		active				
Time (mins)	0	20	40	60	80	100	130	

Table 1. † The order of conditions is randomized. A 2 week washout separates each condition.

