Data collection will be accomplished via case report forms and electronic recording via the devices used in this study. The Principal Investigator will carefully monitor study procedures to protect the safety of research subjects, the quality of the data and the integrity of the study. Participant's data will be de-identified using codes, personal identifiers will be kept separate from study data, and data will be locked in file cabinets or drawers in the TMS laboratory and in the PI's office, if hardcopy, or on a password-protected UAMS server, both located behind locked doors in a restricted access area of the UAMS campus. Only authorized individuals will have access to the code and information that identifies the subjects in this study. Following informed consent to participate, patient's hospital and outpatient records may be reviewed to identify appropriate candidates for the study. Any data obtained as part of the patient's clinical care may be reviewed to determine whether the subject meets inclusion and does not meet exclusion criteria.

Data Analysis

Analyses and Power calculations.

Aims 1 & 2 examine the effect of treatment dose on one primary outcome measure – a difference score between sham and active rTMS in the LMFP of TEPs (Δ LMFP) recorded from TC and DLFC. The analysis plan is the same for both aims. Hierarchical Linear Models (HLMs) will be used due to the nested structure of the design. HLMs will fit the complex covariance structure of the dosing schedule – sham and active tDCS nested within rTMS treatment frequency (1 Hz and 10 Hz). Four primary responses will be estimated, namely Δ LMFP for the sham vs active tDCS and the 1 Hz vs 10 Hz rTMS conditions. From these four responses, four contrasts of interest will be estimated: (1) sham vs active tDCS for 1 Hz rTMS, (2) sham vs active tDCS for 10 Hz rTMS, (3) 1 Hz vs 10 Hz rTMS for sham tDCS, and (4) 1 Hz vs 10 Hz rTMS for active tDCS. An additional 6 contrasts will be used to examine differences in the means for the rTMS post 1 (acute) and post 2 (lasting) time periods. The HLM methodology will estimate the means and standard errors for all these contrasts of interest with a Bonferroni comparison procedure to adjust for the multiple contrasts.

Power Estimates

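### Aims 1 and 2 predict a larger preconditioning effect at 1 Hz than at 10 Hz, but no tDCS-by-frequency contrast is planned; Aim 3's hypothesised LTD–tinnitus correlation has no planned analysis

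*Combined protocol and SAP*

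**What the plan says.** **Hypotheses.** The Protocol Summary (Specific Aim 1) expects a more activated cortex to "facilitate LTD following rTMS at both frequencies of stimulation, but the effect for 1Hz will be stronger for than for 10 Hz". The second aim adopts the same design, analyses and predictions. The Objectives paragraph asks how activation states interact with rTMS dose. For tinnitus patients, the Hypothesis paragraph expects LTD induction to correlate with change in tinnitus perception.

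**Planned analysis, Aims 1 and 2** (Data Analysis, Analyses and Power calculations). Contrasts 1 and 2 compare sham with active tDCS within 1 Hz and within 10 Hz. The other two are listed as "3) 1 Hz vs 10 Hz rTMS for sham tDCS, and (4) 1 Hz vs 10 Hz rTMS for active tDCS". Six more contrasts concern the acute and lasting periods and are not itemised. Then: "The HLM methodology will estimate the means and standard errors for all these contrasts of interest with a Bonferroni comparison procedure".

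**Allocation** (Subject flow). "The first 10 recruited subjects will receive 1Hz rTMS treatment while the second 10 will receive" 10 Hz. Session order and tDCS site are randomised; frequency is not.

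**Power Estimates.** This section says of the published motor-cortex data that "anodal preconditioning induced LTD (a decrease in the MEP amplitude) in both the 1 and 5 Hz conditions" and that "the effect was stronger for 1 Hz than 5 Hz rTMS", without naming the time point.

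**Planned analysis, Aim 3.** Hierarchical models compare mean rating changes with study 109033, and paired t-tests compare LMFP before and after treatment.

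**The concern.** The prediction ranks the size of the preconditioning effect across two frequencies. Each listed contrast fixes one factor and varies the other, so none of the four measures that ranking. The six extra contrasts are described as comparisons over time and do not appear to supply it.

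Two misreadings follow if the plan is applied as written. Contrast 4 taken alone would credit preconditioning with any frequency difference already present without it. And a significant contrast 1 beside a non-significant contrast 2 might be reported as a frequency difference, although it does not test one. The protocol states no such rule, but it does not exclude it.

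Because the 1 Hz and 10 Hz groups are recruited one after the other, contrasts 3 and 4 and the interaction also carry any drift over calendar time. The analysis section does not mention this.

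In Aim 3, two regions and three ratings give six possible correlations with at most ten subjects. With none specified, the choice can be made after seeing the data.

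**Working it through.** **Inputs** (Power Estimates; MEP amplitudes, with 5 Hz standing in for 10 Hz, acute):
- 1 Hz: sham tDCS 0.89, active tDCS 0.64, SD 0.08
- 5 Hz: sham tDCS 0.99, active tDCS 0.98, SD 0.16
- n = 5 per group

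Alpha is not stated; 0.05 two-sided is assumed. The within-subject correlation ρ is not given; 0 to 0.75 is assumed. The protocol says "TEPs have high test-retest reproducibility, particularly when stereotaxic systems are used", which favours the upper part of that range. A value of 0.5 is what three equally correlated, equal-variance sessions give for two Δ LMFP scores that subtract the same sham/sham session.

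**Check against the protocol's own figure.** For contrast 4, SE = √(0.08²/5 + 0.16²/5) = 0.080. An unequal-variance t-test (df 5.9) of 0.98 − 0.64 = 0.34 has power 93.8%; the protocol states 94%.

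**The interaction.**
- Contrast 1 − contrast 2 = (0.89 − 0.64) − (0.99 − 0.98) = 0.25 − 0.01 = 0.24
- Contrast 4 − contrast 3 = (0.98 − 0.64) − (0.99 − 0.89) = 0.34 − 0.10 = 0.24

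**Its precision.** SE = √[2(1 − ρ)(0.08² + 0.16²)/5]. The CI uses df 5.9 (t = 2.459). Power is given for Welch df 5.9 to pooled df 8.

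| ρ | SE | 95% CI | Power at 0.05 | Power at 0.05/12 | Power at 0.05/14 |
|---|---|---|---|---|---|
| 0 | 0.113 | −0.04 to 0.52 | 43–46% | 8–11% | 7–10% |
| 0.5 | 0.080 | 0.04 to 0.44 | 70–75% | 21–28% | 19–25% |
| 0.75 | 0.057 | 0.10 to 0.38 | 94–96% | 49–62% | 45–59% |

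**Can the SE be rebuilt from planned output?** Approximately, from contrasts 1 and 2, which involve different subjects. Not from contrasts 3 and 4: the same subjects appear in both, and treating them as independent gives 0.113 whatever ρ is, against 0.057 at ρ = 0.75.

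**Significant at 1 Hz, not at 10 Hz.** Suppose preconditioning works equally at both frequencies, with the 48% power the protocol states for 1 Hz at 30 minutes. The pattern then arises by chance with probability 0.48 × 0.52 = 0.25 at 0.05. The effect size giving 48% power at n = 5 is about 1.37. At 0.05/12 its power is 11.5%, so the pattern has probability 0.115 × 0.885 = 0.10.

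**Time point.** At 30 minutes the stated effect sizes are 4.80 at 5 Hz and, at 1 Hz, a figure printed as 95%. The latter is either 0.95 or, from the 48% power beside it, about 1.37. No 30-minute SDs are given. If the acute ones applied, the interaction would be between 0.95 × 0.08 − 4.80 × 0.16 = −0.69 and 1.37 × 0.08 − 4.80 × 0.16 = −0.66, opposite in sign to the acute 0.24.

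**Aim 3.** With n = 10, |r| must exceed 0.63 for p < 0.05. An observed r of 0.5 has a Fisher-z 95% CI of −0.19 to 0.86.

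**The case against.** The prediction is loosely worded and could mean contrast 4 alone. Power Estimates gives 94% acute power for exactly that comparison shortly before it says the effect was stronger at 1 Hz. This reading is possible, but the subject of the prediction is facilitation by preconditioning, and the objective is phrased as an interaction. Even on this reading, the plan does not say which contrast answers the hypothesis.

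The gap is also modest. The central hypothesis, facilitation at either frequency, is covered by contrasts 1 and 2. The interaction estimate and an approximate SE can be derived from them, and contrast 3 is planned alongside contrast 4. All of this stands; it limits the point to the frequency ranking and makes the repair easy.

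The 25% figure is close to the maximum of p(1 − p), and the 48% power does not match an effect size of 0.95, which gives 26%. At 26% the chance pattern has probability 0.26 × 0.74 = 0.19 at 0.05 and about 0.04 at 0.05/12. That is a fair qualification. So is the remark that the 0.10 sham-tDCS difference comes from two separate published studies: at n = 5 its CI would be about −0.10 to 0.30.

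Sequential assignment is disclosed in the design sections, so the omission is only that the analysis section does not carry the limitation forward. Aim 3 is an open-label feasibility study, which argues for descriptive correlations, not for leaving the hypothesis without an analysis.

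**Conclusion.** The concern holds and should be fixed. Followed as written, the plan leaves two stated hypotheses without an analysis: the frequency ranking in Aims 1 and 2, and the LTD–tinnitus correlation in Aim 3.

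On the acute planning values, contrast 4 (0.34) exceeds the interaction (0.24) by the 0.10 already present under sham tDCS. These magnitudes are illustrations. They rest on MEP data from motor cortex, on 5 Hz standing in for 10 Hz, and on an assumed within-subject correlation. That the contrast and the correlation are missing depends on none of these, though calling the missing contrast an interaction depends on the reading argued above. Neither added analysis will be precise at these sample sizes, and the interaction cannot separate frequency from recruitment period.

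**What to change.** **Aims 1 and 2** (Specific Aim 1; Analyses and Power calculations):
- Keep contrasts 1 to 4. Add contrast 1 minus contrast 2 from the same hierarchical model, with SE and 95% CI, for TC and DLFC at the acute and lasting times. Name it as the contrast that addresses the frequency hypothesis, reported mainly as an estimate.
- State that a significant contrast 1 with a non-significant contrast 2 will not be taken as support for the ranking.
- State that frequency is assigned sequentially, so contrasts 3 and 4 and the interaction compare non-randomised groups separated in time.
- In Power Estimates, name the time point at which the 1 Hz effect was stronger.

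**Aim 3:** add correlations of LMFP change (TC, DLFC; baseline to after treatment on visit 4) with change in awareness, annoyance and loudness from baseline to the post-treatment rating at visit 4. That is six correlations, each with a 95% CI and labelled descriptive.

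**Cost:** wording only; no new subjects, visits or data. Assuming alpha 0.05 and one family of 4 + 6 = 10 contrasts, the Bonferroni level goes from 0.0050 to 0.0042 with two additions (12), or to 0.0036 with four (14). If every contrast is counted per region, it goes from 0.0025 to 0.0021 (20 to 24). At an effect size of about 1.37, two-sample power for an existing contrast falls from 13.0% at 0.0050 to 11.5% at 0.0042.
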